We are requesting to waive a signature for consent, as the participants will be asked to document consent/assent via REDCap survey, and reaffirm consent/assent verbally prior to the qualitative interview. The surveys and qualitative interview presents no more than minimal risk to the participants. Additionally, we are not asking for any additional personal health information or identifiers apart from Greenphire information. The consent document would be the only other document connecting the survey responses and the PCP. The participants will be provided with an information sheet in recruitment emails and prior to starting the REDCap survey.

We are asking for a waiver of HIPAA authorization. The survey study involves no more than minimal risk to the participant. Additionally, the HIPAA form would be the only other document connecting survey response and the participant. Because we want the participants to be as honest as possible, we do not want the participant to feel that we can connect them to their responses and that connection could include the HIPAA documentation.

PHI will be used 1) to ensure eligibility of participants; 2) to contact for recruitment; and 3) to appropriately describe our sample. We will collect identifiable information (i.e. DOB and address) for those who receive a gift card to process study payment through Greenphire. This data will not be provided to or used for anything aside from payment. As this study will be conducted entirely remotely, it cannot be conducted without access to and use of PHI such as

Subject Completion/Withdrawal

contact information.

Subjects may withdraw from the study at any time without prejudice to their care or employment. The PI may withdraw a participant from the study if it is learned that they did not fulfill eligibility criteria. It will be documented whether or not each subject completes the study.

STATISTICAL CONSIDERATIONS

Evaluation of the Toolkit will focus on Proctor's framework of IS outcomes:⁴⁷

Primary Endpoint

- Penetration (via interrupted time series): via EHR extraction. Rate of scanned NBS results available in the EHR. Rate of documentation and disclosure of NBS and SCT result at < 2 months of age in each of the following: the problem list, the medical history section, and progress note. Evaluate monthly: retrospectively (pre intervention) and prospectively (post intervention).

Secondary Endpoint

- Acceptability: via PCP survey for each toolkit component.

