- Feasibility: Percent of PCPs who use individual toolkit components.
- Adoption/Self-efficacy: PCP survey. Intention and confidence to document/discuss NBS/SCT result.
- Cost: PCP survey: Perceived time (in mins) to document and discuss NBS/SCT result, effect on other discussion topics during the visits.
- Dispersion: Via EHR extraction- Proportion of children over 2 months of age who have NBS/SCT newly documented (as above).
- Knowledge: Caregiver survey- Proportion of caregivers who accurately reported their child's NBS result.
- Inequities in documentation: Via chart review. Demographic data for each infant: primary care site, sex, race, ethnicity, and insurance type.
- Satisfaction: Caregiver survey.

Statistical Methods

Unit of analysis will be the individual PCP (i.e. pre/post) and by trial arm with the primary end point being the rate of documentation and disclosure of NBS and SCT (penetration).

Data will be summarized in numeric and graphic forms. Mean and standard deviation or median and interquartile range will be used for summarizing numerical variables and frequencies and percentages will be used for categorical variables. PCP's EHR documentation and disclosure of newborn screen (NBS) and sickle cell trait (SCT) carrier results will be presented by pre-post intervention as well as by intervention groups. The primary end point of the study is to compare the proportion of PCP's/ EHR documentation and disclosure of NBS and SCT between pre- and post- intervention periods.

Generalized linear mixed effects model will be used for the analysis of the primary end-point. Odds ratio with confidence interval will be provided for the documentation and disclosure. Generalized linear mixed effects model will also be used to compare the proportion of post-intervention documentation and disclosure over time (monthly) between two intervention groups. Mean score of acceptability for each intervention (A, B, C) as well as mean total score for all three interventions will be compared between two intervention groups. Similarly, other survey results such as Self-Efficacy of PCP to document NBS and time cost will be compared between two intervention groups. Also, dispersion, caregiver knowledge and caregiver satisfaction will be

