compared between two groups. Two sample t-test, Mann-Whitney U-test, Chi-square test, analysis of variance (ANCOVA), liner mixed effects model, logistic regression, and mixed effects logistic regression will be used, for the above comparisons, as appropriate. PCP nested within clinic will be used as the random effects in the model as needed. All tests will be two-tailed with an overall level of significance of 0.05. Benjamini-Hochberg method will be used to adjust the level of significance for multiple comparisons. Statistical software packages SPSS, SAS (version 9.4) or latest version of R will be used for the analysis.

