Sample Size Justification: This is a pilot study and there is no reported effect size on the intervention of this study in the literature. Therefore, the main goal of this study is to explore reliable effect size that would assist designing future studies with formal hypothesis testing. The primary aim of the study is to increase PCP's EHR documentation and disclosure of NBS and SCT carrier results during infancy (age less than 1 month). It has been found in a chart review that 71% of newborns over the last 3 years had a newborn screen result scanned into their chart. The goal of this study is to raise this to 90%. A sample size of 74 in each of the pre- and post-intervention period can detect the targeted difference in newborn screen of 19% with 86% power at the level of significance of 0.05. PCP documentation has been reported as 20% in the literature. We aim to raise this 50%. Again, a sample size of 43 in each of the pre- and post-intervention period would be adequate to detect the targeted difference in the PCP documentation with a power of 85% at the level of significance of 0.05. Currently 53% sickle cell traits has been documented. Once again, the goal is to raise this to 90%. A sample size of 21 infants with sickle cell traits (SCT) in each of pre- and post-intervention periods would be adequate to detect this difference in this documentation with a power of 80% at the level of significance of 0.05. In DE, the prevalence of SCT is 2.1% in overall children and about 7% in African Americans. Considering 2.1% SCT in overall children, we need 1000 infants to screen in each of the pre-and post-intervention periods, to detect the targeted difference with a power of 80% at the level of significance of 0.05. The study plans to recruit 10 PCPs in each of the intervention arm (20 PCP in both arms). About 6-10 infants are expected to be seen by a PCP in a month and 54-90 new infants are expected to be seen by a physician during 9 months of post intervention period. We expect that minimum of $540 \times 2 = 1080$ patients (540 for each intervention) to be seen by 20 PCPs. Therefore, a minimum sample size of 1080 infants is planned for each of the pre-and post-intervention periods for this study. The planned minimum sample size of 1080 in the post intervention period would also be adequate to determine the effect size for survey results and documentation and disclosures for each intervention arm separately.

Analysis of Qualitative Data:

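### The primary endpoint is labelled an interrupted time series, but the primary pre/post odds ratio has no calendar-time term named, so as stated it mixes the toolkit effect with any background drift

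*Combined protocol and SAP*

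**What the plan says.** - **Design and endpoint.** Study Objectives and General Schema of Study Design call the trial a two-arm randomised interrupted time series. Primary Endpoint reads "Penetration (via interrupted time series): via EHR extraction" and adds "Evaluate monthly: retrospectively (pre intervention) and prospectively (post intervention").
- **Primary analysis.** Statistical Methods compares "EHR documentation and disclosure of NBS and SCT between pre- and post- intervention periods" with a generalized linear mixed model and an odds ratio. It lists no fixed effects. On random effects it says "PCP nested within clinic will be used as the random effects in the model as needed".
- **The one model with time.** A second mixed model will "compare the proportion of post-intervention documentation and disclosure over time (monthly) between two intervention groups".
- **Results by arm.** Documentation and disclosure "will be presented by pre-post intervention as well as by intervention groups". Sample Size Justification expects enough infants to size survey results and "documentation and disclosures for each intervention arm separately".
- **Baselines and targets.** For newborn-screen (NBS) scanning, "71% of newborns over the last 3 years had a newborn screen result scanned into their chart", with a goal of 90%. PCP documentation is to go from 20% to 50%, and documentation of sickle cell trait (SCT) from 53% to 90%.
- **Period lengths.** Duration of Study Participation gives about 5 months per site; Sample Size Justification assumes 9 post-intervention months. No pre-period length is given for the EHR endpoint. The caregiver-survey text mentions retrospective windows of 6 and 3 months.

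**The concern.** An interrupted time series uses the pre-period series to project what would have happened without the intervention. A two-period contrast uses only the two period averages, so any trend already under way counts as effect.

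Nothing else in the plan separates the two. Both arms receive the toolkit, so the pre/post contrast has no untreated concurrent control. The post-only monthly model compares randomised arms and is largely protected from a trend common to both, but it answers all-in versus add-in, not toolkit versus none. Splitting by arm keeps partly exposed add-in infants out of the all-in odds ratio, yet each arm's ratio still contains the drift. Random effects do not remove a trend. Control of Bias and Confounding covers social desirability and qualitative coding only.

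This bears on the pilot's main product. Study Objectives states the main goal as a reliable effect size, and the pre/post odds ratio is that effect size. The 71% baseline is one figure for three years, so the documents cannot show that the background is flat.

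**Working it through.** **1. The plan's own power figures.** Arcsine formula: power = Φ(h·√(n/2) − 1.96), with h = 2·asin√p2 − 2·asin√p1.
- 71% to 90%, n = 74: h = 0.494, power 85.2% (stated 86%).
- 20% to 50%, n = 43: h = 0.644, power 84.7% (stated 85%).
- 53% to 90%, n = 21: h = 0.867, power 80.2% (stated 80%).

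All three reproduce as plain two-period tests with no trend and no clustering. That shows how the study was sized; it does not settle what the analysis model will contain.

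**2. Spurious odds ratio.** Assumptions: linear drift of s points per month, baseline equal to the pre-period mean, no toolkit effect. Apparent difference = s × (pre + post)/2 months. With s = +0.5 and a 6-month pre-period:

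| Months | Difference | NBS from 71% | OR | PCP documentation from 20% | OR |
|---|---|---|---|---|---|
| 6+5 | 2.75 points | 73.75% | 1.15 | 22.75% | 1.18 |
| 6+9 | 3.75 points | 74.75% | 1.21 | 23.75% | 1.25 |

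The target odds ratios are (0.90/0.10)/(0.71/0.29) = 3.68 and (0.50/0.50)/(0.20/0.80) = 4.0. The spurious log odds ratio is therefore 11-16% of target (for example ln 1.148/ln 3.68 = 0.106 and ln 1.246/ln 4.0 = 0.159).

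Range: at s = 0.25 the OR is 1.07-1.12 over these two layouts. At s = 0.5 it runs from 1.10-1.13 (3+5 months) to 1.26-1.30 (9+9). With s = −0.5 at 6+5 the rates become 68.25% and 17.25%, giving OR 0.88 and 0.83, so a benefit would be hidden by a similar amount.

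**3. Rejection at nominal 5%, s = +0.5, clustering ignored.** Accrual from the plan: 20 PCPs × 6 infants per month = 120 per month, so 6+5 months gives 720+600.
- 720+600, NBS: pooled p = 0.7225, SE = √(0.7225 × 0.2775 × (1/720 + 1/600)) = 0.0248, z = 1.11, rejection 20%. PCP documentation: 23%.
- 1080 per period in 6+9 months: z = 0.0375/0.0191 = 1.96 for NBS, rejection 50%. PCP documentation: 56%.

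A layout with 1080 infants in 5 post-intervention months is not used. It needs 1080/(20 × 5) = 10.8 infants per PCP per month against the stated 6-10.

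**4. Precision of a time-adjusted model.** Expected information; terms for arm, linear time, an all-in step, and add-in steps at 0, 6 and 12 weeks; instant uptake; no clustering. For NBS, the 95% CI factor for the all-in change goes from ×/÷1.55 (crude, all-in arm) to 1.92 at 720+600, and from 1.40 to 1.74 at 1080 per period (6+9). At 720+600, SE = ln 1.92/1.96 = 0.333, so power = Φ(1.302/0.333 − 1.96) = 97%. PCP documentation is no lower. With a 3-month pre-period (360+600) NBS power is 84%. With a slope change added at 720+600 it is 89%. SCT has about 1080 × 2.1% = 23 infants per period, and all-in power would be 20-23%.

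**5. Gradual uptake.** Assumption: no drift, effect rising over 2 months on the logit scale to the target. For a plateau of 3.68 (NBS), the step-only adjusted all-in OR is about 2.1 (6+5) and 2.3 (6+9). The crude OR is 2.67 and 3.05; the post-period average effect is 2.84 and 3.18. For PCP documentation (plateau 4.0) the adjusted OR is about 2.0 and 2.3, the crude 3.09 and 3.47, and the average 3.03 and 3.43.

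**The case against.** **Silence is not exclusion.** No fixed effects are listed, the endpoint carries the time-series label, and a mixed model could include month. This stands. A reader might infer that the sponsor has decided against adjusting for time; the documents do not say so. What they lack is a written primary model that matches the label.

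**The drift is hypothetical.** This stands too. No rate or direction is given, so the figures above illustrate sensitivity and are not evidence that drift exists.

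**The bias is small beside the noise.** In simulations with the target effect and +0.5 points per month, the crude all-in NBS odds ratio is 4.26-4.49 for a true 3.68, a factor of 1.16-1.22. That lies inside the crude interval factor of 1.40-1.55. It limits the severity, but a later trial planned on the point estimate would inherit the bias. Rejection rates matter less than bias in a pilot meant to size an effect, although Statistical Methods does set a two-sided 0.05 level.

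**A step-only time-adjusted model can do worse than the crude ratio.** This is the strongest objection, and item 5 of the working bears it out. Gradual uptake is plausible: the plan describes repeated reminders and office hours, and it measures use of the components as an outcome. So the adjusted step cannot simply replace the crude odds ratio.

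**Conclusion.** The concern holds, and it should be fixed. The plan's design label and its stated primary contrast do not match, and the stated contrast cannot separate the toolkit effect from drift. At an assumed 0.5 points per month the distortion is an odds ratio of about 1.15-1.25 with a 6-month pre-period. That is enough to raise nominal 5% rejection to 20-56%, but it is modest against targets of 3.68 and 4.0. These figures rest on the assumed drift rate, a pre-period length borrowed from the caregiver-survey text, linear drift, and independent infants.

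Two stronger readings are not supported. A reader might infer that the randomised all-in versus add-in comparison is compromised; the defect is confined to the pre/post contrast, overall and by arm. A reader might also infer that the crude odds ratio should give way to an adjusted step; under gradual uptake the step can be further from the truth.

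**What to change.** Before fixing the number of monthly points, reconcile the post-period length (about 5 months against 9) and state the pre-period length for the EHR endpoint. Then, in Statistical Methods:

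- For NBS scanning and PCP documentation, add an infant-level logistic mixed model with calendar month of first well visit, arm, arm-specific exposure terms taken from the study phase already recorded for each infant, and PCP-within-clinic random effects.
- Report its all-in estimate beside the crude pre/post odds ratios, overall and by arm. State that the crude ratio is not adjusted for trend and should not alone be carried forward as the effect size.
- Do not rest on an instant step. Pre-specify one version with a slope change and one that treats the first 1-2 months after all-in roll-out as a transition period. For the slope version, name the month at which the effect will be read.
- Report the add-in A, B and C steps as exploratory.
- Keep the planned SCT pre/post comparison, labelled as unadjusted for trend, because about 23 infants per period cannot support the adjusted model.

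The data are already to be collected, so the cost is analysis work and a wider interval: for NBS about ×/÷1.92 instead of 1.55 at 720+600. Instant-step power stays at about 97% or more with a 6-month pre-period and is about 84% for NBS with 3 months. It will be lower with gradual uptake or a transition period. These figures ignore clustering, and they are optimistic if site-level shocks occur with only two sites per arm.

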Increasing Documentation and Disclosure of Sickle Cell Trait Status: An Implementation Science Approach

NCT05387564

Document Date: September 1, 2023
Updated cover page: October 21, 2025

Increasing Documentation and Disclosure of Sickle Cell Trait Status: An Implementation Science Approach: SCTalk

COMPLIANCE STATEMENT

This study will be conducted in full accordance with all applicable Nemours Research Policies and Procedures and all applicable Federal and state laws and regulations including 45 CFR 46. All episodes of noncompliance will be documented.

The investigators will perform the study in accordance with this protocol, will obtain consent, and will report unanticipated problems involving risks to subjects or others in accordance with Nemours IRB Policies and Procedures and all federal requirements. Collection, recording, and reporting of data will be accurate and will ensure the privacy, health, and welfare of research subjects during and after the study.

STUDY OBJECTIVES

A two-arm, randomized, interrupted time series design will compare an “all-in” and “add-in” approach to a suite of intervention strategies to increase PCP’s EHR documentation and disclosure of NBS results and SCT status during infancy. This is a pilot study. The main goal of this pilot study is to establish a reliable estimate of the effect size of a suite of intervention strategies.

Primary Objectives (Aim)

Using an implementation framework we will assess and compare the acceptability, feasibility, self-efficacy, and time costs of using the intervention strategies when delivered “all-in” versus “add-in” by measuring the following outcomes.

- Acceptability: via PCP survey for each toolkit component.
- Feasibility: Percent of PCPs who use individual toolkit components.
- Adoption/Self-efficacy: PCP survey. Intention and confidence to document/discuss NBS/SCT result.
- Cost: PCP survey: Perceived time (in mins) to document and discuss NBS/SCT result, effect on other discussion topics during the visits.
- Penetration (via interrupted time series): via EHR extraction. Rate of scanned NBS results available in the EHR. Rate of documentation and disclosure of NBS and SCT result at < 2 months of age in each of the following: the problem list, the medical history section, and progress note. Evaluate monthly: retrospectively (pre intervention) and prospectively (post intervention).

Secondary Objective (Aim)

[figure not shown]

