Assess the effects of the intervention strategies when delivered “all-in” versus “add-in” by measuring the following outcomes.

- Dispersion: Via EHR extraction- Proportion of children over 2 months of age who have NBS/SCT newly documented (as above).
- Knowledge: Caregiver survey- Proportion of caregivers who accurately reported their child's NBS result.
- Inequities in documentation: Via chart review. Demographic data for each infant: primary care site, sex, race, ethnicity, and insurance type.
- Satisfaction: Caregiver survey.

INVESTIGATIONAL PLAN: Overview

General Schema of Study Design

A two-arm, randomized, interrupted time series design will compare an “all-in” and “add-in” approach. In the “all-in” arm, participants receive all toolkit components at once. In the “add-in” arm, participants will have “multiple interruptions” with sequential addition of components in 6 week increments (**Figure – replace 3 month label with 6 week label**). This will allow for exploration of the added benefit of certain components as compared to the whole toolkit.

Toolkit Components:

- 1) Intervention A: EHR “nudge” within the birth history and/or well-child progress note template
- 2) Intervention B: “lunch-and-learn” sessions (in person or pre-recorded per office preference)
- 3) Intervention C: written educational materials (i.e. post cards, poster, PDF files) to alert PCPs to the importance of SCT documentation and “talking points” to facilitate disclosure;

Duration of Study Participation

Duration of study participation for a site will last a total of approximately 5 months. During the 5 months, PCPs will participate in 4 surveys (15 minutes each) and 1 qualitative interview (30 minutes). Study duration of caregivers will be for survey completion (5-10 minutes).

Total Number of Study Sites/Total Number of Subjects Projected

- 1) Sites: At least 2 sites per arm of the study with at least 10 PCPs in each arm are required.
- 2) PCPs: All PCPs from a given office will be eligible for participation. This will result in at least 20 Nemours PCPs at 4 or more office locations in the Delaware Valley. PCP offices will be purposively chosen to include a wide racial distribution within their patients.
- 3) Caregivers: 500 caregivers of infants with SCT or a normal NBS who are cared for within the specified office location.

Study Population

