Practice level data from the medical record. For each practice location: Patient level demographics (based on having been seen for a well child exam in the 3 years prior to data extraction) will be linked with the primary practice location at the start of the trial. Practice level data will be obtained from a retrospective evaluation of available EHR data and focus on.

- Age and gender distribution
- Race and Ethnicity distribution
- Insurance make-up (Private, Medicaid, other)
- Zipcode to assess median household income of patients seen at that location (census data), Childhood Opportunity Index (COI)
- Number and portion of the patient population with SCT documented in the problem list, medical history section, and diagnosis codes

PCP Consent and Demographic Survey:

Toolkit components will be available to PCPs and office staff in all trial sites regardless of their participation in the research portion of the trial. Use of the toolkit components is as an educational aid and to facilitate routine patient care.

PCPs will initially be approached for consent for the research portion of the trial prior to toolkit initiation. For PCPs who elects to participate in the longitudinal research portion of the trial, a general demographic survey will be completed at time of initial consent. The demographic survey will be facilitated by REDCap and administered electronically. PCPs may enroll at any time during the trial though first attempt at consent will be before toolkit initiation at with each toolkit component rollout and survey point.

“Roll-out” of toolkit components:

- “All-in” arm: The “all-in” trial arm will have access to and be educated regarding the intervention components at one time point via email, via discussion at lunch & learn, via office meeting, or via virtual meeting or recording (depending on site preference).
- “Add-in” arm: Each PCP in the “add-in” arm will receive the intervention components in the same sequence (within a 1 month timeframe of other offices in the “add-in” arm) with 1 component added every 6 weeks.

With each toolkit component rollout an email will be sent to the office staff reminding them about the project, alerting them to the new component, and notifying them about a virtual Teams “office hours” where the study PI will be available for questions or concerns. The study PI will also be available for any virtual or in-person education an office site may request (ie at an office meeting, etc)

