PCP Implementation Surveys: PCPs will receive surveys by email (through REDCap) every 6 weeks. Survey is expected to take 15 minutes to complete. For PCPs in the “all-in” arm, the first survey will be sent prior to the intervention “roll-out” and every 6 weeks after that. For PCPs in the “add-in” arm, the first survey will be sent prior to intervention A “roll-out”, intervention B “roll-out”, intervention C “roll-out”, and then 6 weeks after. The survey is created specifically for this study and focused on the acceptability of using the intervention component, feasibility of using the intervention component, the opportunity costs of using the intervention component (the time it takes to use the intervention, the perceived effect on other discussion topics with well child visits), and the intention and confidence (i.e. self-efficacy) to document and discuss NBS and SCT results.

PCP Qualitative Interviews: At completion of the Intervention period, PCP participants will be contacted to schedule the qualitative interview. Interviews will be expected to last ~30 minutes. Interviews will be completed over the telephone or using a video conferencing platform. If video conferencing is used, participants will be instructed to keep their camera turned off, so their image will not be recorded. The participant will be notified verbally when the recording has started and when it has stopped.

The qualitative interviews will assess their experience with the components and intention to document and disclose NBS/SCT results in the future.

Infant Identification:

Infants seen at a participating site during the retrospective and intervention period for a well child visit before 2 months of age will be identified through EHR data extraction on a rolling basis (i.e. once a month during the trial) based on ICD10 code for a new patient/well child exam (ICD 10: Z00.110, Z00.111, Z00.121, Z00.129, Z00.00, Z00.01 or CPT: 99381, 99382, 99383, 99384, 99385, 99391, 99392, 99393, 99394, 99395).

Documentation and Discussion of NBS/SCT results for all infants identified: via chart review. For each infant identified, the following data will be collected via EHR extraction and manual chart review:

- Email
- Preferred language
- MRN (to facilitate manual chart review)
- Gender
- Race, ethnicity
- Insurance
- Zipcode (to assess Childhood Opportunity Index)
- Phase of study they were first seen for a WCC (retrospective, “all-in” A/B/C, Intervention A, Intervention B, Intervention C)

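### The pooled primary pre/post odds ratio counts the add-in arm's roughly 12 weeks on a partial toolkit as post time, so it understates the full-suite effect whenever component B or C adds benefit

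*Combined protocol and SAP*

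**What the plan says.** Study Objectives gives the purpose: "The main goal of this pilot study is to establish a reliable estimate of the effect size of a suite of intervention strategies". Sample Size Justification repeats that the effect size is meant for designing later studies.

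Statistical Methods defines the primary end point as a comparison of "documentation and disclosure of NBS and SCT between pre- and post- intervention periods", analysed with a generalized linear mixed model and reported as an odds ratio. The Primary Endpoint entry fixes the two periods: "Evaluate monthly: retrospectively (pre intervention) and prospectively (post intervention").

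The all-in arm receives every component at one time point. For the add-in arm, the General Schema describes "sequential addition of components in 6 week increments", and the roll-out text has each PCP starting on one component, "with 1 component added every 6 weeks". The chart-review list records for each infant the "Phase of study they were first seen for a WCC", but no model in Statistical Methods mentions that variable.

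Two post-period lengths can be read from the plan. Under Duration of Study Participation: "Duration of study participation for a site will last a total of approximately 5 months". Under Sample Size Justification: "54-90 new infants are expected to be seen by a physician during 9 months of post intervention period".

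**The concern.** The goal is the effect of A, B and C together, but the primary contrast has two levels. In the add-in arm, post time begins when A alone is released and the whole suite is in place only from week 12. A pooled pre/post odds ratio therefore averages three contrasts against no toolkit: A, A+B and A+B+C. If B or C contributes anything, the average is closer to the null than the full-suite effect.

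The effect size is this pilot's main product. A later trial planned on the pooled figure would take over a number that depends partly on how long this pilot's add-in sites spent in the build-up, which is a feature of the roll-out schedule and not of the suite.

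**Working it through.** **The plan's own count.** 10 PCPs × 6 infants per month × 9 months = 540 per arm, and 540 × 2 = 1080, as stated. The add-in arm contributes its full 540, so no A or A+B time is set aside. At the stated 2.1% prevalence, 1080 × 0.021 = 22.7 infants with SCT.

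**Share of post time on a partial toolkit.** Add-in time before C is 6 + 6 = 12 weeks. For a post period of T weeks, the add-in share is 12/T. With equal, even infant flow in the two arms, the pooled share is w = (12/T)/2.

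**Dilution.** Let p0 be the pre rate, p1 the full-suite rate, and f the average fraction of the full gain reached during the A and A+B phases. Then

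pooled post rate = p0 + (p1 − p0) × [1 − w(1 − f)].

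The documents do not give f, so two cases are shown. If the three components add equally on the proportion scale, f = (1/3 + 2/3)/2 = 0.5. If only C works, f = 0. There is no dilution only if f = 1, that is, if A alone produces the whole gain. The rates are the plan's targets, 20% to 50% for PCP documentation and 71% to 90% for scanned results. Their full-suite odds ratios are (0.50/0.50)/(0.20/0.80) = 4.00 and (0.90/0.10)/(0.71/0.29) = 3.68.

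**Worked case, 9 months (39 weeks), 20% to 50%.** w = (12/39)/2 = 0.154.
- Equal gains: 0.20 + 0.30 × (1 − 0.154 × 0.5) = 0.477, so the odds ratio is (0.477/0.523)/0.25 = 3.65.
- Only C: 0.20 + 0.30 × (1 − 0.154) = 0.454, so the odds ratio is 3.32.

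Pooled odds ratios under each post-period length:

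| Post period | Add-in share | Pooled share w | 20% to 50% (full 4.00): equal / only C | 71% to 90% (full 3.68): equal / only C |
|---|---|---|---|---|
| 9 months (39 weeks) | 31% | 15% | 3.65 / 3.32 | 3.16 / 2.75 |
| 5 months (21.7 weeks) | 55% | 28% | 3.39 / 2.86 | 2.83 / 2.27 |
| 18 weeks | 67% | 33% | 3.27 / 2.67 | 2.69 / 2.09 |

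The 18-week row is the span from the first to the fourth PCP survey (3 × 6 weeks). The plan does not state it as a post period, and it is shown only as a short-period bound.

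**Add-in arm alone, 9 months, 20% to 50%.** Here the share is 12/39 = 0.308. Equal gains give 0.20 + 0.30 × (1 − 0.308 × 0.5) = 0.454, odds ratio 3.32. Only C gives 0.20 + 0.30 × (1 − 0.308) = 0.408, odds ratio 2.75.

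**All-in arm alone.** Partial-toolkit time is zero, so the odds ratio is undiluted.

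**Infants on the full toolkit.**
- 9 months: 540 + 540 × (1 − 12/39) = 540 + 374 = 914, of whom 914 × 0.021 = 19.2 with SCT.
- 5 months: 300 + 300 × (1 − 12/21.7) = 300 + 134 = 434, of whom 9.1 with SCT. All 600 post infants would give only 12.6.

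**The case against.** The strongest reply is that the plan already yields an undiluted suite estimate. Statistical Methods calls for analysis and presentation by arm, and Sample Size Justification says the sample is adequate to determine effect sizes for each arm separately. This stands. A reader might infer that the plan cannot estimate the suite effect at all; that is too strong. What remains is that the all-in odds ratio is not named as the primary estimate, and the pooled and add-in figures are mixed.

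Second, the mixed model's fixed effects are not listed. The endpoint is labelled an interrupted time series, and the General Schema speaks of multiple interruptions in the add-in arm. A reader might infer that the sponsor chose to leave exposure phase out; the documents do not show that. But the label specifies no phase term, and the only primary contrast written down has two levels. The further monthly model compares the arms within post time and gives no A+B+C versus none estimate.

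Third, an add-in pre/post odds ratio that includes the build-up is a legitimate effect of add-in delivery. That is fair: the figure is diluted only as an estimate of the full suite, which is what the main goal names.

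Fourth, phase is recorded at the first well visit, while the outcome runs to 60 days and a phase lasts 42 days. Exposure level also tracks calendar time in the add-in arm, and pooling all A+B+C time merges the two delivery modes. These points stand, and they limit what simple recoding can deliver.

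**Conclusion.** The concern holds for the pooled primary odds ratio and for the add-in odds ratio; it does not hold for the all-in odds ratio. On the 9-month period behind the sample size the dilution is moderate: about 3.65 or 3.32 against 4.00, and about 3.16 or 2.75 against 3.68. It grows as the post period shortens. A reader might take the 18-week values (about 3.3 and 2.7 against 4.0) as the expected size, but neither stated duration supports that.

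The direction is certain if B or C adds benefit. The size rests on equal and even infant flow, on the assumed component shares, and on the plan's targets standing in for the true full-suite effect. That A and A+B time counts as post is read from the retrospective/prospective definition together with the 540 infants counted in the add-in arm; no single sentence defines it. The change should be made before analysis, because the effect size is the pilot's stated product.

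**What to change.** - In the primary mixed model, replace the single pre/post indicator with cumulative exposure in four levels: none, A, A+B, A+B+C. Name A+B+C versus none as the primary suite effect size.
- Report that contrast separately for the all-in arm as well. Report A and A+B versus none as exploratory.
- State how an infant whose 60-day outcome window spans two 42-day phases is classified, and add a sensitivity analysis excluding such infants.
- Reconcile the 5-month and 9-month durations, since the size of the dilution and the infant counts both depend on them.
- Relabelling the add-in phase codes to show cumulative exposure is optional.

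No new data are needed. The cost is precision: at 9 months about 914 of the 1080 post infants inform the headline contrast, so its interval widens. The stated targets of 74 and 43 per period are still met. Infants with SCT fall from about 23 to about 19, below the stated 21, so SCT power or precision should be restated. The sensitivity analysis will have fewer still.
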